RQ3: What is the impact of providing the training and support to both YPSWs and SSWs on YP’s involvement with the criminal justice system, measured using youth cautions and convictions data in the SSDA903?

RQ4: What is the impact of providing the training and support to both YPSWs and SSWs on YP’s episodes missing from care² as reported in the SSDA903?

RQ5: What is the impact of providing the training and support to both YPSWs and SSWs on the internalising and prosocial subscales of the SDQ, completed by FCs/supported lodgings providers at baseline and follow-up.

YPSWs and SSWs

RQ6: What is the impact of providing the training and support to both YPSWs and SSWs on their attitudes towards TIP, measured using the ARTIC scale?

Foster carers

RQ7: What is the impact of providing the training and support to both YPSWs and SSWs on the compassion satisfaction, burnout, and secondary traumatic stress of FCs/caregivers in a family setting, measured using the ProQOL?

RQ8: What is the impact of providing the training and support to both YPSWs and SSWs on the FCs’ attitudes towards TIP, measured using a bespoke questionnaire that builds upon other TIP surveys.

Although the intervention is being delivered to YPSWs and SSWs, the trial primarily focuses on the measurement of the impact of the intervention on eligible YP. For a YP to be in scope for the trial, the young person needs to meet the basic age criteria (10-17), but also needs to have both a YPSW and SSW that is in-scope for the trial. If some YPSWs or SSWs are excluded from the trial (which can, for example, happen if Independent Fostering Agencies (IFAs) are excluded in some LAs) then the YP they are assigned to is not included in the trial.

Within each LA, the YPSWs and SSWs eligible for the trial are:

¹ That is, administrative data that is collected via the ‘Children looked after return’.

² Missing from care: a looked-after child who is not at their placement or the place they are expected to be (for example school) and their whereabouts is not known.

1. YPSWs whose caseload includes at least one young person aged 10 to 17 at the start of the trial;
2. SSWs working with a FC or supported lodgings provider with an eligible YP in their care at the start of the trial.

Design overview

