Four secondary outcomes for YP are making use of standard administrative data collected for the SSDA903. We expect to have close to complete data on these outcomes for all YP who stay in foster care.

Table 1: Trial design

Trial design, including number of arms		Two-armed cluster randomised controlled trial
Unit of randomisation		Young person’s social worker (YPSW)
Stratification variables (if applicable)		Local Authority (LA)
Primary outcome	variable	Young person’s externalising behaviour
	measure (instrument, scale, source)	Externalising score, Strengths and Difficulties Questionnaire (Goodman, Meltzer & Bailey, 1998), carer-reported version, fielded in online survey 10-12 months after baseline
Secondary outcome(s)	variable(s)	Young person: SDQ Internalising and Prosocial sub-scales; Involvement with criminal justice system; transition into residential care, placement stability; missing from care episodes SSW / YPSW: Attitudes to trauma-informed practice FCs: compassion satisfaction, burnout; secondary traumatic stress; attitudes to trauma-informed practice
	measure(s) (instrument, scale, source)	Young person: SDQ, carer-report version; Child conviction or subject to youth caution (SSDA903 2024-25); transition into residential care (SSDA903 2024-25); unplanned moves (SSDA903 2024-25); missing from care episodes (SSDA9035 2024-25). SSW / YPSW: ARTIC scale at 12 month after baseline FCs: Professional Quality of Life Scale (self-report), bespoke questionnaire (self-report) at 10-12 months after baseline
Baseline for primary outcome	variable	Young person’s externalising behaviour
	measure (instrument, scale, source)	Externalising score, Strengths and Difficulties Questionnaire, carer-report (Goodman et al, 1998), fielded in online survey as close as possible to randomisation of YPSW

Baseline for secondary outcome	variable	
Young person: Emotional and behavioural difficulties; Involvement with criminal justice system; Transition into residential care, placement stability; missing from care episodes
 
SSW / YPSW: Attitudes to trauma-informed practice
 
FCs: compassion satisfaction; burnout; secondary traumatic stress; attitudes to trauma-informed practice

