This approach to randomisation does not give a four-arm RCT with balance across all four arms. Analysis Arms 1 and 2 will be balanced (which is vital for the primary analysis), and Arms 3 and 4 will be balanced, but the YP in Arms 3 and 4 will have different experiences to those in Arms 1 and 2 in the sense that the Arms 3 and 4 YP will be more likely to have a YPSW and SSW who work together infrequently. This does not affect the primary analysis, which compares just Arms 1 and 2, but in the exploratory analysis that compares all four arms the lack of balance will be acknowledged.

Once randomisation has been completed, each young person will have been assigned to one of the four randomisation arms. Some contamination during the trial is inevitable (with some 'control' YP being assigned to a trained social worker during the trial and vice versa). This will be monitored and sensitivity analysis will be conducted to establish the degree to which this dilutes the overall effect sizes (see analysis section).

Sample size calculations overview

Our primary analysis (which uses externalising behaviour as measured through the SDQ as an outcome) focuses on the YP where both the YPSW and SSW have either been assigned to the intervention group or to the control group (Analysis Arms 1 and 2 as described in the randomisation section above). Arms 1 and 2 between them cover 66% of all the eligible YP identified as in-scope for the trial.

Table 2 sets out the MDES and sample sizes that were originally anticipated and as they were presented in version 1 of the trial protocol. The final column sets out our revised estimates after recruitment of LAs, baseline data collection, and randomisation. The original intention was to recruit 10 LAs to the trial rather than the eight achieved, and the initial predictions of response rate at baseline proved too optimistic. However, the number of social workers was much larger than anticipated, which reduces the average cluster size. Nevertheless, the MDES

has increased from the initial protocol estimate of 0.21 standard deviations to 0.24 standard deviations.

The assumptions behind the calculations are:

- Across the eight LAs, the total number of eligible YP is 1,477. Of these, 979 have been assigned to one of the two primary analysis arms: 458 to the group where both the YPSW and the SSW are assigned to the intervention group and 521 to the group where both the YPSW and the SSW are assigned to the control group.

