If, at the analysis stage, the average cluster size proves to be very close to one (that is 1.1 or below) we will use a single-level model rather than two-level. In this case the model will be:

$$Y_{ik} = \beta_0 + \beta_1 Group_{ik} + \beta_2 X_{ik} + \beta_3 LA_k + \varepsilon_{ik} \quad (\text{Eq 2})$$

where

Y_{ik} =externalising score at follow-up for young person i within LA k ;

$\beta_0, \beta_1, \beta_2, \beta_3$ = fixed effect parameters;

$Group_{ik}$ = indicator variable for group allocation of the YP's YPSW and SSW (0=control; 1=intervention) within LA k ;

X_{ik} = baseline externalising score for young person i within LA k ;

LA_k = a vector for the local authority dummy variables, of which there will be seven. β_3 is a coefficient vector for the LA dummy covariates;

ε_{ik} = residual error term.

Secondary outcome analysis

There are a range of secondary outcome measures reflecting the fact that the Theory of Change suggests that impacts should be observed for all the groups potentially affected by the SW training, namely YP, FCs, and the social workers themselves.

1. Young people

There are six secondary outcomes for YP:

- The SDQ internalising score (continuous variable);
- The SDQ prosocial score (continuous variable);

and four outcomes taken from SSSA903 data:

- One or more unplanned moves (binary);

- Transition into residential care (binary);
- Conviction or subject to youth caution (binary);
- Any missing from care episodes (binary).

2. Foster carers

There are four secondary outcomes for foster carers (detailed in the trial protocol):

- The three Professional Quality of Life (ProQOL) subscales (continuous variables):
 - o compassion satisfaction;
 - o burnout;
 - o secondary traumatic stress.
- Knowledge and understanding of TIP score (continuous).

3. Social workers

For social workers in the trial, there is just one secondary outcome:

- ARTIC score (continuous)

The analysis of the secondary outcomes will be conducted following similar overall model specifications as the primary outcome analysis, but with some modifications to reflect the nature of the data. These are:

- The models for the binary outcomes will be logistic regressions rather than linear;
- For the SSDA903 outcomes, for YP just entering foster care there will be no applicable baseline data. To account for this, a baseline outcome will be included in the model coded as categorical: present, absent; not applicable.

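### RQ4 asks about episodes missing from care, but only any-versus-none is analysed; one supporting analysis of episode frequency would be a cheap improvement

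*SAP*

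**What the plan says.** RQ4 (SAP, Introduction) is about "episodes missing from care² as reported in the SSDA903". Table 1 (Design overview) names the follow-up measure as "missing from care episodes (SSDA9035 2024-25", and its baseline row uses the same term for the previous year. The list of outcomes at the start of the SAP says only that the outcome is missing from care.

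Under Secondary outcome analysis, 1. Young people, the variable becomes "Any missing from care episodes (binary". On the model: "The models for the binary outcomes will be logistic regressions rather than linear". On the covariate for the SSDA903 outcomes: "a baseline outcome will be included in the model coded as categorical: present, absent; not applicable".

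No other part of the SAP uses the number of episodes. The sections on switching, missing data, compliance and the four-arm analysis add no count or rate analysis. The SAP states neither the expected share of young people with an episode nor the expected number per young person.

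**The concern.** A young person can go missing more than once in a year. Under the planned coding, one episode and ten score the same, both in the outcome and in the baseline covariate. Two consequences follow.

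- If training makes episodes less frequent among young people who still go missing at least once, the share with any episode does not change. The planned test then rejects only at its false-positive rate. This follows from the definition of the variable and needs no assumed rate.
- If training lowers the episode rate in general, some young people move to zero and the binary test picks up part of the effect. The rest of the information is lost.

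What is at stake is how RQ4 can be worded in the report. A null odds ratio for any episode does not show that episodes were unaffected. The primary outcome is untouched.

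**Working it through.** **The plan's own figure.** The SAP formula with 183 and 208 young people, cluster size 1.5, ICC 0.2 and correlation 0.6 gives 2.8 × √[(1/183 + 1/208) × 1.10 × 0.64] = 0.238, which matches the stated 0.24. The figure of about 0.20 sd for SSDA903 outcomes cannot be reproduced, because the SAP says its ICC and correlation are not known. It is in any case a standardised difference and does not bear on the choice between binary and count.

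**Inputs from the SAP (Sample size calculations overview).** 458 young people in Arm 1 and 521 in Arm 2, so at most 458 + 521 = 979; two-sided 5% level.

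**Inputs assumed, because the SAP has none.** Control share with any episode p₀ of 5–30%; negative binomial counts with size parameter k of 0.1–1 (smaller k means more repeats); no clustering, baseline adjustment or Hochberg correction.

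**Formulas.** Control mean μ₀ = k[(1 − p₀)^(−1/k) − 1]. With rate ratio RR, μ₁ = RR·μ₀ and p₁ = 1 − (1 + μ₁/k)^(−k). Var(log RR) = (1/458)(1/μ₁ + 1/k) + (1/521)(1/μ₀ + 1/k).

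**Worked case: p₀ = 20%, k = 0.2, RR = 0.6.**
- μ₀ = 0.2 × (0.8^(−5) − 1) = 0.410, or 0.410/0.20 = 2.05 episodes per young person who goes missing. μ₁ = 0.246 and p₁ = 0.148.
- Binary: z = 0.0517/√(0.148 × 0.852/458 + 0.2 × 0.8/521) = 0.0517/0.0241 = 2.14; power about 57%.
- Count: variance = 9.063/458 + 7.437/521 = 0.0341, SE 0.185; z = 0.511/0.185 = 2.77; power about 79%.
- With a design effect of 1.24, which is what 0.20 sd implies at zero correlation ((0.20/0.179)² = 1.24), these become 48% and 70%.

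**Simulation, 40% cut in the rate** (3,000 replicates; score tests on any-versus-none and on the mean count; null rejection about 5% for both):

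| p₀, k | Binary | Count | Gain, points |
|---|---|---|---|
| 5%, 1 | 33% | 33% | about 1 or less |
| 10%, 1 | 57% | 61% | 4 |
| 10%, 0.5 | 54% | 59% | 4–5 |
| 10%, 0.1 | 33% | 46% | 13 |
| 15%, 0.2 | 54% | 68% | 14 |
| 20%, 0.5 | 78% | 87% | 9 |
| 20%, 0.2 | 56% | 78% | 22 |
| 30%, 0.2 | 53–55% | 87% | about 33 |

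**Second and later episodes halved, same young people ever missing.** The binary test rejects 4–6% of the time throughout. Count power is 5% (10%, k = 1), 17% (10%, k = 0.1), 20% (15%, k = 0.2), 17% (20%, k = 0.5), 39% (20%, k = 0.2) and 79% (30%, k = 0.2).

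**Training only stops young people ever going missing** (share with any episode × 0.7). The binary test is better: 54% v 38% (15%, k = 0.2) and 91% v 55% (30%, k = 0.2), up to 36 points.

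**Sample size.** Data collection excludes young people who leave foster care entirely, except for the outcomes that capture moves. Missing from care does not appear to be one of these, so the analysed number is below 979 and absolute power is lower than shown for both tests.

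**The case against.** The plan can fairly be defended. RQ4 does not say number, rate or frequency, the opening outcome list says only missing from care, and any-versus-none is a clear definition treated like the other three SSDA903 outcomes. A reader might infer that the SAP contradicts itself or that logistic regression is wrong here. The documents do not support that: the binary form is one legitimate reading of RQ4, it resists distortion by a few young people with very many episodes, and its rationale may sit in the protocol.

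The count is also not uniformly better. It loses by up to 36 points under one plausible mechanism, gains almost nothing where repeats are rare, and is itself weak in most settings where only repeats fall. The SAP does not say which mechanism to expect. All of this stands, and it is why the count should be added and should not replace the planned outcome.

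A reader might also infer that any fall in repeat episodes goes undetected, or that RQ4 will be reported as no impact. The first is strictly true only if the set of young people with any episode is unchanged. The second is not in the SAP, which promises effect sizes with confidence intervals and p-values.

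What remains is narrow: nothing in the plan addresses frequency, and RQ4 as worded invites that reading.

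**Conclusion.** A cheap improvement confined to RQ4, one of six Hochberg-corrected secondary outcomes for young people. There is no bias, no invalid test and no effect on the primary conclusion.

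The certain part is definitional: the planned variable carries no information on frequency among young people with at least one episode. The size is conditional. Across the settings run, a count analysis gains about 1 to 33 points of power for a 40% cut in the rate. That rests on assumed prevalence, dispersion and effect type, on full numbers of 458 v 521, and on ignoring clustering. Adding a supporting model while keeping the binary outcome avoids having to guess the mechanism.

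**What to change.** In Secondary outcome analysis, before outcome data are examined:

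1. Keep the binary outcome and its place in the Hochberg family unchanged.
2. Add one supporting analysis of the number of episodes: a negative binomial or Poisson model with standard errors clustered on YPSW, LA fixed effects, the baseline count with an indicator for not applicable, and a log time-in-care offset if the SSDA903 extract holds it. The SAP does not say that the extract holds counts or days in care, so check this first.
3. Report the rate ratio and its confidence interval beside the odds ratio.
4. Word the RQ4 conclusion so that the binary result speaks only to whether any episode occurred. No rule tying a no-impact conclusion to the two results jointly is needed; without a stated criterion it would decide nothing.

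Timing matters because the Randomisation section says the analysis will not be blind to allocation, so a count model added later would look data-driven. If episode counts prove unusable, the minimum is to reword RQ4 to any episode and give the reason.

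Cost: a paragraph and one model. Downside: one supporting estimate outside the multiplicity correction, sensitive to a few young people with many episodes.

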The trial is being run as a two-arm cluster randomised controlled trial with random allocation at the level of the YPSW. Each SSWs is assigned to the same group as the YPSW with which they work most frequently. The unit of analysis for the primary outcome is the YP. As is explained in more detail in the randomisation section, **the randomisation leads to a trial with four arms as follows, but only the first two of the arms are to be used in the main trial analysis**³: (i) YP where both the YPSW and SSW are assigned to the training; (ii) YP where neither the YPSW nor the SSW are assigned to the training; and (iii) YP where the YPSW is assigned to the training but the SSW is not; and (iv) YP where the SSW is assigned to the training but the YPSW is not. This document focuses on the main trial analysis of the first two arms. Analysis that incorporates all four arms is described in the final section of this document 'Analysis of all four arms of the trial'.

Data collection

Data for the trial is being collected at two points in time, at baseline (prior to randomisation of the YPSWs) and at a follow-up point 10 to 12 months later, via online surveys directed at the in-scope YPSWs and SSWs, and FCs. The SDQ data for YP is being collected via the online surveys sent to the FCs. Social Worker involvement in the trial is not dependent on FCs agreeing to complete the surveys, so there is inevitably a fairly high percentage of missing data for YPs and FCs at both baseline and follow-up. Likewise, social workers are randomised to intervention or control irrespective of whether they complete a baseline or follow-up questionnaire.

FCs will be asked to complete a follow-up questionnaire to cover their own outcomes even if their eligible YP is no longer in their care. In cases where a YP moves to another FC, the new FC will be asked to complete the SDQ at follow-up. If a YP moves out of foster care entirely they will be excluded from the trial analysis, the exception being the secondary outcomes that capture moves. Social workers will be asked to complete follow-up questionnaires even if they have changed jobs, but we expect the response rate for movers to be low.

³ As is described later in the randomisation section, this is because the four arms are not all equivalent, with the first and second arms being balanced, and the third and fourth, but without balance across between the first/second and third/fourth arms.

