As noted, the primary trial analysis will focus on YP within ‘Analysis Arms’ 1 and 2 (that is, pure intervention and pure control). Young people in Arms 3 and 4 will be excluded from the primary analysis. Arms 3 and 4 will however be included in an exploratory analysis, where the impact of just one of the two YPSWs/SSWs being assigned to the intervention is estimated. This is described in the final section ‘Analysis of all four arms of the trial’.

The randomisation method aims to maximise the sample size for the primary analysis. Each SSW was assigned to a ‘unique YPSW’ prior to the start of the trial, with this being done by assigning each SSW to the YPSW with whom they share the most eligible YP. To illustrate, if a SSW has 10 eligible YP, and for five of the 10 they work alongside YPSW-1, for three they work with YPSW-2, and for two they work with YPSW-3, then this SSW is assigned to YPSW-1.⁵ If YPSW-1 is then randomly allocated to the intervention group, this SSW will also be assigned to the intervention group (and vice versa). Note that two or more SSWs might be assigned to a single YPSW under this model. The aim in doing this assigning is to generate a set of YPSW/SSW ‘clusters’ that between them cover as many eligible YP as possible. The randomisation steps are described in detail in the Appendix.

The steps in the randomisation are summarised below:

Step 1	Assign each SSW to a unique YPSW (the one they work with for most YP)
Step 2	Randomly allocate YPSW to either intervention and control
Step 3	Assign each SSW to ‘intervention’ or ‘control’ with the allocation being the same as the allocation to group of their ‘unique YPSW’
Step 4	Having determined the group status for every YPSW and SSW, establish which of four arms each YP now belongs to:

⁵ With assignment to an SSW being done randomly if there are two or more SSWs with which they share the same number of families.

	
Arm 1 : Both of the YP's SSW and YPSW assigned to intervention;
 
Arm 2 : Both of the YP's SSW and YPSW assigned to control;
 
Arm 3: The YP's SSW assigned to intervention but their YPSW assigned to control
 
Arm 4: The YP's SSW assigned to control but their YPSW assigned to intervention.
 
Only those in Arms 1 and 2 are used in the primary analysis.

--	---

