where

n_1 is the achieved sample size in the intervention arm (Group 1);

n_2 is the achieved sample size in the control arm (Group 2);

m is the average cluster size;

ρ is the ICC; and

R is the correlation between the baseline and follow-up score.

The value 1.96 is the z-value for a type 1 error rate (alpha) of 0.05, and 0.84 is the z-value for 80% power.

Table 2 sets out the assumptions for the primary outcome (externalising SDQ score). The assumptions do not all hold for the secondary outcomes, the major differences being:

- For SSDA903 outcomes which are collected via administrative systems, the sample sizes will be somewhat larger because losses to the sample will be lower. The correlation between baseline and follow-up is not known but is likely to be low for the non-SDQ scores at least, and the ICC is not known, but overall we expect an MDES of around 0.20sd for these outcomes;
- There will be fewer FCs than YP in the analysis as FCs may care for more than one eligible YP, our best current assumption being that it will be around 139 in Group 1 and 163 in Group 2. We estimate an MDES of 0.27sd for their outcomes.
- There are 422 YPSWs and 264 SSWs in the trial (686 overall), divided into two groups, intervention and control, with around 316 in the intervention arm and 370 in the control arm per arm (139 and 163 respectively after non-response). For their outcomes we estimate an MDES of around 0.23sd.

Table 2: Sample size calculations

	Protocol version 1	Post randomisation
Minimum Detectable Effect Size (MDES)	0.21 sd	0.24 sd

		Protocol version 1	Post randomisation
Pre-test/ post-test correlations	level 1 (participant)	0.6	0.6
	level 2 (cluster)	0	0
Intracluster correlations (ICCs)	level 1 (participant)	0	0
	level 2 (cluster)	0.2	0.2
Alpha ⁷		0.05	0.05
Power		0.8	0.8
One-sided or two-sided?		Two	Two
Average cluster size		7.7	1.5
Number of clusters ⁸	intervention	70 YPSWs	198 YPSWs/124 SSWs at randomisation stage
	control	70 YPSWs	224 YPSWs/140 SSWs at randomisation stage
	total	140 YPSWs	422 YPSWs/264 SSWs
Number of participants	intervention	540	183 (after non-response)
	control	540	208 (after non-response)
	total	1,080	391

⁷ Please adjust as necessary for trials with multiple primary outcomes, 3-arm trials etc. when a Bonferroni correction is used to account for family-wise errors.

⁸ Please adjust as necessary e.g., for trials that are randomised at the setting, practitioner or participant level.

Analysis

Primary outcome analysis

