- The regression model for social worker outcomes will be specified using the primary outcome model, but there will be no clustering effects for YPSWs given that these are the units of randomisation. Here the model will be:

$$Y_{jk} = \beta_0 + \beta_1 Group_{jk} + \beta_2 X_{jk} + \beta_3 LA_k + \varepsilon_{jk} \quad (\text{Eq 3})$$

where

Y_{jk} = ARTIC score at follow-up for SW j within LA k;

$\beta_0, \beta_1, \beta_2, \beta_3$ = fixed effect parameters;

$Group_{jk}$ = indicator variable for group allocation (0=control; 1=intervention) within LA k;

X_{jk} = baseline ARTIC score for SWj within LA k;

LA_k = a vector for the local authority dummy variables, of which there will be seven. β_3 is a coefficient vector for the LA dummy covariates;

ε_{jk} = residual error term.

Given the large number of secondary outcomes, the secondary outcome tests for YP will be corrected for multiple comparisons using Hochberg's step-up procedure⁹. Likewise, but independently, the tests for the four secondary outcomes for FCs will be corrected.

Subgroup analyses

The trial is relatively small, with an expected sample size of under 210 per arm with complete baseline and follow-up data on the primary outcome. There are no prior expectations of large differential impacts across sub-groups of YP, and the sample size is too small for modest differences across groups to be identified. For these reasons, very little sub-group analysis is planned. The exception is that the primary YP outcome will be presented split by ethnic group (generated by running separate regression models per sub-group) to facilitate future meta-analysis, but excluding any ethnic groups with less than 30 YP per arm.

For the secondary social worker outcome, ARTIC, a joint YPSW/SSW analysis will be undertaken but, subject to some evidence of impact, separate models will be run and presented for YPSWs and SSWs.

Further analyses of the primary trial data

Sensitivity of the effect sizes to changes in YP and FC social workers during the trial

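### The unclustered ARTIC model (Eq 3) is justified for YPSWs only, but it also includes SSWs who inherit their YPSW's allocation; the joint and SSW-only models should be clustered on the randomised YPSW

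*SAP*

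**What the plan says.** The Design overview describes a "two-arm cluster randomised controlled trial with random allocation at the level of the YPSW". SSWs are not randomised separately. Under Randomisation, each SSW is first tied to the YPSW with whom they share the most eligible young people, and then takes that YPSW's allocation (Steps 1 to 3). The section adds: "Note that two or more SSWs might be assigned to a single YPSW under this model".

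Under Secondary outcome analysis, the ARTIC model (Eq 3) contains group, baseline ARTIC, LA dummies and one residual. It has no random effect, because "there will be no clustering effects for YPSWs given that these are the units of randomisation". Subgroup analyses states that for ARTIC "a joint YPSW/SSW analysis will be undertaken", with separate YPSW and SSW models only if there is some evidence of impact. The Compliance section adds a separate CACE analysis for ARTIC.

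The Sample size section counts 422 YPSWs and 264 SSWs (686 workers), expects 139 and 163 in the two arms after non-response, and says: "For their outcomes we estimate an MDES of around 0.23sd". Nowhere does the SAP give a random effect, robust standard error or other clustering correction for ARTIC.

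**The concern.** The reason given for dropping the cluster level is sound for a model of YPSWs alone, since each YPSW is one randomised unit. It does not extend to SSWs. In the joint model a YPSW and the tied SSWs share one random allocation but are treated as separate independent observations. In an SSW-only model the same happens wherever two or more SSWs follow one YPSW.

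Correlation within a unit is plausible. Workers are tied because they share the most young people, and the programme aims to improve communication between these two groups of staff. The LA dummies remove only differences between authorities.

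ARTIC is the only outcome for RQ6. The Hochberg correction is specified for the young-person and foster-carer outcomes, so ARTIC is read at the nominal 5%. The joint result also decides whether the separate YPSW and SSW models are run. Too small a standard error would therefore affect both the reported result and that decision.

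**Working it through.** **1. The plan's own figure.** The SAP formula is MDES = 2.8 × √[(1/n1 + 1/n2) × (1 + (m − 1)ρ) × (1 − R²)].
- Primary outcome (183 and 208, m = 1.5, ρ = 0.2, R = 0.6): 0.238, agreeing with the stated 0.24.
- Social workers (139 and 163, R = 0.6, no clustering): 0.259, not the stated 0.23. No R is stated for ARTIC. With no clustering, 0.23 requires R of about 0.70 (0.231).

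So 0.23 cannot be reproduced from stated inputs. Below it serves only as a baseline to be scaled.

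**2. Randomised units.** 422 + 264 = 686 workers in 422 units, a mean of 686/422 = 1.63 workers per unit.

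**3. The SAP's Appendix example.** SSW003 shares most young people with YPSW12, and SSW010 with YPSW04. SSW008 has one each with YPSW12, YPSW01, YPSW04 and YPSW06, and ends in control. Of those four, only YPSW12 and YPSW04 are control, so SSW008 follows one of them and shares a randomised unit with SSW003 or SSW010.

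**4. Unit size among responders.** The expected response is p = (139 + 163)/686 = 302/686 = 0.440. Assume workers respond independently. Responders per unit average 302/422 = 0.716. Dividing by the chance that a unit has at least one responder gives the mean size of the units that appear in the analysis.
- SSWs spread at random: chance of no responder = 0.560 × exp(−0.440 × 264/422) = 0.560 × 0.759 = 0.425; mean size = 0.716/0.575 = 1.24.
- At most one SSW per YPSW: 0.560 × (1 − 0.626 × 0.440) = 0.406; mean size = 0.716/0.594 = 1.20.

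Both exceed 1.1, the limit at or below which the SAP allows a single-level model for the primary outcome.

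**5. Design effect, joint model.** Design effect = 1 + (expected responding fellow members of a worker's unit) × ICC.
- Random spread: the size-weighted mean unit is (1.626² + 0.626)/1.626 = 2.010, so 1.010 fellows, of whom 1.010 × 0.440 = 0.445 respond.
- At most one SSW per YPSW: 264 pairs and 158 singles give (264 × 4 + 158)/686 − 1 = 0.770 fellows, of whom 0.339 respond.

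True two-sided type I error = 2 × [1 − Φ(1.96/√DE)]. No ICC is given for ARTIC, so the range is an assumption; 0.2 is the SAP's value for the SDQ score. With random spread and expected non-response:

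| ICC | Design effect | True SE ÷ model SE | Type I error | MDES 0.23 becomes |
|---|---|---|---|---|
| 0.05 | 1.02 | 1.01 | 5.3% | 0.233 |
| 0.1 | 1.04 | 1.02 | 5.5% | 0.235 |
| 0.2 | 1.09 | 1.04 | 6.0% | 0.240 |
| 0.3 | 1.13 | 1.06 | 6.6% | 0.245 |

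At ICC 0.2 with at most one SSW per YPSW: 1 + 0.339 × 0.2 = 1.07, type I error 5.8%. At ICC 0.2 with all 686 responding, the design effect is 1.15 to 1.20 and type I error 6.8% to 7.4%.

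**6. Simulation.** An unclustered two-group test with 422 randomised YPSWs and 264 inheriting SSWs, at ICC 0.2, rejected in 5.9% of null trials with non-response and 6.9% with full response (6,000 runs each). With all SSWs concentrated on 150 YPSWs the rates were 6.4% and 8.7%.

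**7. SSW-only model.** With random spread, an SSW has 263/422 = 0.623 fellow SSWs on the same YPSW, of whom 0.623 × 0.440 = 0.274 respond. At ICC 0.2 the design effect is 1.05 and type I error about 5.6%.

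**The case against.** The strongest reply is that the practical effect is small. About 302 workers, not 686, are expected in the analysis, and non-response turns most units into singletons. The ICC of 0.2 was chosen for young people's SDQ scores, on the argument that social workers influence those scores; it does not carry over to agreement in attitudes between two professionals. Eq 3 also adjusts for each worker's baseline ARTIC and for LA, which may absorb part of any shared variance. All of this stands. It limits the size but does not make the stated reason apply to SSWs.

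Three stronger readings are tempting, and the SAP does not support them:
- A reader might infer that the ARTIC test is certainly anti-conservative, by the 7% or more that applies to all 686 workers. That needs full response and a substantial positive ICC. The SAP expects 44% response and gives no ARTIC ICC; with an ICC near zero there is no inflation.
- A reader might infer that every ARTIC model is wrong. The YPSW-only model is not, since there each observation is a randomised unit.
- A reader might infer that the missing YPSW/SSW indicator confounds the joint estimate. By Table 2, 198/422 = 46.9% of YPSWs and 124/264 = 47.0% of SSWs are in the intervention arm. Worker type is almost unrelated to allocation, so leaving it out costs at most some precision.

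**Conclusion.** Wrong as written. The justification for Eq 3 does not cover the SSWs in the joint model, nor an SSW-only model in which SSWs share a YPSW, and nothing else in the SAP corrects this. That follows from the text alone.

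The size depends on two quantities the SAP does not give: the within-unit correlation of ARTIC after adjustment, and how SSWs are distributed over YPSWs. With random spread and independent response at the expected rate, the joint test's true type I error lies between about 5.3% and 6.6% for ICCs from 0.05 to 0.3. This is a modest fault in one secondary outcome. It has no bearing on the primary analysis, whose Eq 1 has a YPSW random effect.

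**What to change.** In the paragraph introducing Eq 3, confine the reason for having no cluster term to the YPSW-only model. For the joint and SSW-only models, give each SSW the identifier of the tied YPSW (each YPSW carries its own) and state that cluster-robust standard errors on that identifier will be used. Apply the same to the ARTIC CACE analysis. Naming one method in advance matters. Robust standard errors suit these data better than a random intercept, whose variance would be weakly identified when most units have a single responder.

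A YPSW/SSW indicator may be added to the joint model for precision; it is optional. The assumed R, ICC and unit size behind the 0.23 MDES should be stated alongside it.

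The cost is a few lines of SAP text and a small change to the analysis code. No new data are needed: the ties were set before allocation, so the identifier should already be in the randomisation file.
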